### 13.12. Table of Contents for Tables, Listings, and Figures

The table of contents for tables, listings, and figures will be provided in a corresponding mock shell document.

Sponsor: Boston Pharmaceuticals, Inc.

Protocol Number: BOS161721-02

SAP Version and Date: Version 3.0, 13Nov2020

### 13.13. Other SAP(s) Describing Analyses not Covered in the SAP

SAPs describing analyses (pharmacokinetics [PK], PK/pharmacodynamics[PD], etc.) not covered within this SAP will be included within this Appendix.

**BOS161721-02: A RANDOMIZED DOUBLE-BLIND PHASE 1b/2  
COMBINED STAGGERED MULTIPLE DOSE ESCALATION STUDY OF  
BOS161721 IN SYSTEMIC LUPUS ERYTHEMATOSUS (SLE) PATIENTS  
ON A BACKGROUND OF LIMITED STANDARD OF CARE**

## ABBREVIATIONS

|                  |  |
|------------------|--|
| ACR              | American College of Rheumatology               |
| ADA              | Anti-drug antibody                             |
| AE               | Adverse event                                  |
| AESI             | Adverse event of special interest              |
| ANA              | Antinuclear antibody                           |
| ANCOVA           | Analysis of covariance                         |
| ANOVA            | Analysis of variance                           |
| APL              | Antiphospholipid                               |
| AUC              | Area under the curve                           |
| BICLA            | BILAG-based Composite Lupus Assessment         |
| BILAG            | British Isles Lupus Assessment Group           |
| BP               | Blood pressure                                 |
| C3               | Complement C3                                  |
| C4               | Complement C4                                  |
| C L   | Systematic clearance                           |
| CLASI            | Cutaneous Lupus Area and Severity Index        |
| C max | Maximum plasma concentration                   |
| CPAP             | Clinical Pharmacology Analysis Plan            |
| CS               | Corticosteroid                                 |
| CSR              | Clinical study report                          |
| C-SSRS           | Columbia Suicide Severity Rating Scale         |
| CTCAE            | Common Terminology Criteria for Adverse Events |
| CV               | Coefficient of variation                       |
| DLT              | Dose-limiting toxicity                         |
| DMC              | Data Monitoring Committee                      |
| dsDNA            | Double-stranded deoxyribonucleic acid          |
| ECG              | Electrocardiogram                              |
| CCI              |  |
| FAS              | Full analysis set                              |
| HR               | Hazard ratio                                   |
| IA               | Interim Analysis                               |
| IEC              | Independent Ethics Committee                   |
| IL-21            | interleukin 21                                 |
| IRB              | Institutional Review Board                     |
| ISR              | Injection site reaction                        |
| IWRS             | Interactive web response system                |
| LLN              | Lower limit of normal                          |
| LLOQ             | Lower limit of quantification                  |
| MAD              | Multiple Ascending Dose                        |
| MedDRA           | Medical Dictionary for Medical Affairs         |
| nAb              | Neutralizing antibody                          |
| NCI              | National Cancer Institute                      |
| PD               | Pharmacodynamics                               |

Sponsor: Boston Pharmaceuticals, Inc.  
Protocol Number: BOS161721-02  
SAP Version and Date: Version 2.0, 29Nov2018

|            |   |
|------------|---|
| PGA        | Physician's Global Assessment                                     |
| PK         | Pharmacokinetics  |
| POC        | Proof of concept  |
| PP         | Per protocol set  |
| pSTAT3     | Phosphorylated signal transducer and activator of transcription 3 |
| PT         | Preferred Term  |
| SAD        | Single ascending dose   |
| SAE        | Serious adverse events  |
| SAP        | Statistical analysis plan   |
| SAS        | Statistical analysis system                                       |
| SC         | Subcutaneously  |
| CCI |   |
| SLE        | Systemic Lupus Erythematosus                                      |
| SLEDAI-2K  | SLE Disease Activity Index 2000                                   |
| SLICC      | Systemic Lupus International Collaborating Clinics                |
| Sm         | Smith   |
| SOC        | System Organ Class  |
| SRI-4      | SLE Responder Index 4   |
| SRI-5      | SLE Responder Index 5   |
| SRI-6      | SLE Responder Index 6   |
| SS         | Safety analysis set   |
| SSA        | Sjögren syndrome-A (Ro)   |
| SSB        | Sjögren syndrome-B (La)   |
| $t_{1/2}$  | Terminal elimination half-life                                    |
| TEAE       | Treatment emergent adverse event                                  |
| $T_{max}$  | First time to maximum concentration                               |
| TTMF       | Time to medication failure  |
| ULN        | Upper limit of normal   |
| $V_d$      | Volume of distribution  |
| WHO        | World Health Organization   |

## 1. INTRODUCTION

The statistical analysis plan (SAP) details the planned analyses that will be included in the Clinical Study Report (CSR) of study number BOS161721-02: A Randomized Double-Blind Phase 1b/2 Combined Staggered Multiple Dose Escalation Study of BOS161721 in Systemic Lupus Erythematosus (SLE) Patients on a Background of Limited Standard of Care. The content of this SAP is based on the protocol Version 4.0 (Amendment 3) dated 27July2018.

Revision Chronology:

V1.0

05SEP2018

Original

## 2. STUDY OBJECTIVES AND ENDPOINTS

### 2.1. Multiple Ascending Dose (MAD) Phase 1b Study

| Objectives   | Endpoints   |
|--|---|
| 
Primary
 

• To assess safety, tolerability, and immunogenicity of repeat doses of BOS161721 (20, 60, and 120 mg) administered subcutaneously (SC) in adult patients with moderately to severely active SLE on limited background standard of care treatment, in order to estimate the optimal dose.

 | 
Safety Endpoints
 

• Incidence and severity of adverse events (AEs) and serious adverse events (SAEs), related AEs, AEs leading to study drug discontinuation, AEs by severity and relatedness

• Injection site reactions

• Columbia Suicide Severity Rating Scale (C-SSRS)

• 12-lead electrocardiograms (ECGs) parameter results at each visit and change from baseline

• Vital signs (blood pressure [BP], heart rate, and temperature) parameter results at each visit and change from baseline

• Clinical laboratory results and change from baseline

• Physical examinations changes from baseline

• Anti-drug antibodies (ADAs)

• Study drug exposure/compliance

 |

|   |   |
|---|---|
| 
Secondary
 
 
• To characterize the PK of BOS161721 and select the optimal dose of BOS161721 based on safety, PK, and PD effects in patients with mild to moderate SLE.
 
 | 
Pharmacokinetic (PK) Endpoints
 
 
• BOS161721 concentration by visit and time point
 
• Maximum observed concentration (<math>C_{max}</math>), first time to maximum concentration (<math>T_{max}</math>), area under the concentration-time curve (AUC), <math>t_{1/2}</math>, systematic clearance (<math>C_L</math>), volume of distribution (<math>V_d</math>)
 
 
Pharmacodynamic (PD) Endpoints
 
 
• Results and changes (or shifts) from baseline to each visit in phosphorylated signal transducer and activator of transcription 3 (pSTAT3), C3 and C4 levels, and leukocyte immunophenotype
 
• Results and changes (or shifts) from baseline in anti-double-stranded DNA (dsDNA), antinuclear antibodies (ANA), anti-Sjögren syndrome A and B (SSA, SSB), Smith (Sm), and antiphospholipid (APL) autoantibodies at each visit
 
• Results and changes (or shifts) from baseline in abrogation of IL-21 gene signature at each indicated visit
 
 |
| 
Exploratory
 
 
• CCI
 
    | 
CCI
    |

## 2.2. Proof of Concept (POC) Phase 2 Study

| Objectives   | Endpoints  |
|--|--|
| Primary  |  |
| 

To demonstrate a superior effect of BOS161721 at the chosen dose compared with placebo for response on the SLE Responder Index 4 (SRI-4)

 | 
Primary Efficacy Endpoint
 

The proportion of patients with a SRI-4 response at Day 210

 |

|   |   |
|---|---|
| 
Secondary
 
 
• To demonstrate a superior effect of BOS161721 at the chosen dose compared with placebo for response on clinical indicators of SLE activity, in adult patients with moderately to severely active SLE on limited background standard of care treatment
 
 | 
Secondary Efficacy Endpoints
 
 
• The proportion of patients with:             
 
- SRI-4 response at each visit
 
- SRI-5 and SRI-6 response at each visit
 
- a sustained reduction of oral corticosteroid (CS) (<math>\leq</math> 10 mg/day and <math>\leq</math> Day 0 dose) between Day 120 and Day 210
 
- new BILAG A flare or <math>></math> 1 BILAG B flares relative to baseline through Day 210
 
- PGA worsening
 
- a BICLA response
 
- a CLASI response
 
- medication failures
 
 
 
• Results and changes from baseline in:             
 
- CLASI
 
- swollen and tender joints ACR-28
 
- SLEDAI-2K
 
- SLICC/ACR damage index
 
 
 
• Time to medication failure
 
• Duration of longest SRI-4 response
 
• Time to first SRI-4 response
 
• Time to BILAG A flare or <math>></math> 1 BILAG B flare compared to baseline through Day 210
 
 |
| 
Safety
 
 
• To assess safety and tolerability of repeat doses of BOS161721 (20, 60, and 120 mg) administered SC in adult patients with moderately to severely active SLE on limited background standard of care treatment
 
  | 
Safety Endpoints
 
 
• Incidence and severity of adverse events (AEs) and serious adverse events (SAEs), related AEs, AEs leading to study drug discontinuation, AEs by severity and relatedness
 
• Injection site reactions
 
• C-SSRS
 
• 12-lead ECGs parameter results at each visit and change from baseline
 
• Vital signs (blood pressure [BP], heart rate, and temperature) parameter results at each visit and change from baseline
 
  |

|   |  |
|---|--|
|   | 

• Clinical laboratory results and change from baseline

• Physical examinations changes from baseline

• ADAs

• Study drug exposure/compliance

 |
| Exploratory   |  |
| 

• CCI

 | 

• CCI

  |
| 

• CCI

 | 

• CCI

  |
| 

• CCI

 | 

• CCI

  |

The order in which the endpoints for this trial will be discussed in subsequent sections is based on the phase 2 POC portion of the study. The phase 1b MAD endpoints will also be discussed within the context of the phase 2 POC portion of the study but will appear out of the specified order in the above table in an effort to maintain common concepts across both phases in one location within the SAP.

### 3. STUDY DESIGN

#### 3.1. Study Design and Population

This is a Phase 1b/2 combined, randomized, multicenter, double-blind, placebo-controlled trial to study the clinical efficacy, safety, and pharmacokinetics (PK) of subcutaneously (SC) doses of BOS161721 in adult patients with moderately to severely active SLE. After successfully

Sponsor: Boston Pharmaceuticals, Inc.  
Protocol Number: BOS161721-02  
SAP Version and Date: Version 2.0, 29Nov2018

completing a screening phase, eligible patients will be randomized to a specified dose of BOS161721 or placebo. The dosing schedule will be monthly.

The trial will consist of 2 double blinded- portions: MAD Phase 1b and POC Phase 2. Patients may receive a total of 7 SC monthly doses of study drug on Days 0, 30, 60, 90, 120, 150, and 180, followed by safety/efficacy follow-up visit at Days 210, and safety follow up visits at Days 240, and 270.

SLE disease activity assessment data will be centrally reviewed by medical monitor and sponsor to ensure the scores are clinically meaningful and compliant with specific definition. The scope of responsibility includes, but is not limited to, review and confirmation of “A” and “B” British Isles Lupus Assessment Group (BILAG) system organ disease, confirmation of clinical components of the SLE Disease Activity Index 2000 (SLEDAI-2K) score at screening and during the study, and cross validation- of the instruments used in this study to assess the disease activity. Further details on the content and methods of data reports by the medical monitor and sponsor will be outlined in the Medical Data Review Plan along with the processes and procedures that will be followed.

### 3.1.1. Multiple Ascending Dose Phase 1b

The MAD portion will consist of 3 cohorts:

- Cohort 1 (20 mg SC) will include 6 patients
  - 5 patients will receive BOS161721 (active group) and 1 patient will receive placebo (placebo group)
- Cohorts 2 (60 mg SC) and 3 (120 mg SC) will include 12 patients each
  - 9 patients in the active group and 3 in the placebo group

Doses selected for each of the 3 cohorts is based on a 90-day safety, tolerability, PK and PD data review from the Phase 1 single ascending dose (SAD) study (BOS161721-01) in healthy subjects. All doses selected for the MAD part of the study are projected not to exceed the mean exposure of that achieved in the SAD study.

The MAD portion of the study design is staggered, where after the 6 patients in Cohort 1 have received 2 doses and have completed 2 weeks of follow up- after the second dose, Cohort 2 begins dosing (after the data monitoring committee (DMC) evaluation of the safety and tolerability data from Cohort 1). Similarly, after 8 of the 12 patients in Cohort 2 have received 2 doses and have completed 2 weeks of follow up- after the second dose, Cohort 3 begins dosing after the DMC evaluation of the safety and tolerability data from Cohorts 1 and 2. Each cohort will continue at their assigned dose level through their respective 6-month treatment periods (See Study Schematic in the study protocol). If patients discontinue the study in a cohort prior to adequate safety follow-up, he/she may be replaced.

Criteria for dose escalation are further described in the DMC Charter.

### 3.1.2. Proof of Concept Phase 2

[figure not shown]
The optimal dose is chosen based on MAD Phase 1b safety, tolerability, immunogenicity, and PK and PD data. The dose will be communicated by a letter to site investigators participating in the POC Phase 2 portion, and to the Institutional Review Board / Independent Ethics Committee (IRB/IEC).

For the POC part of the study, approximately 156 additional patients will be randomized to active or placebo groups in a 2:1 ratio.

As in the MAD part of the study, each patient in the POC portion may receive a total of 7 SC monthly doses of study drug on Days 0, 30, 60, 90, 120, 150, and 180. Assessments will be completed according to the Schedule of Assessments detailed in the study protocol. Dose selection will be based on the DMC and sponsor's assessment of safety, tolerability, immunogenicity, and PK and PD data from the MAD portion of 30 patients treated with BOS161721/placebo.

DMC safety reviews will be conducted periodically throughout the study as described in the DMC charter.

### Study Diagram for MAD Phase 1b and POC Phase 2

A = active drug (BOS161721); P = placebo

### 3.2. Randomization and Blinding

This is a randomized, double-blind study.

Patients meeting all inclusion and exclusion criteria will be centrally randomized to either placebo or BOS161721 using an IWRS according to a randomization list generated by an independent, non-study statistician. Randomization will be performed separately for each study portion and separately for each cohort in the Phase 1b and 2 portions as follows:

| Phase/Cohort      | Number of Patients | Randomization Ratio BOS161721:Placebo |
|-------------------|--------------------|---------------------------------------|
| Phase 1b/Cohort 1 | 6                  | 5:1                                   |
| Phase 1b/Cohort 2 | 12                 | 3:1                                   |
| Phase 1b/Cohort 3 | 12                 | 3:1                                   |
| Phase 2           | 156*               | 2:1                                   |

\*Additional patients may be enrolled to ensure sufficient numbers of patients are in the full analysis set (FAS).

Eligible patients will be assigned to the study portion which is active at time of enrollment. Similarly, patients in the Phase 1 MAD will be assigned to the cohort which is active. Each patient will be assigned a unique randomization number which will not be reused.

All patients, investigators, and study team participants will be blinded to treatment assignment. An independent biostatistician not otherwise involved on the study will be unblinded and prepare materials for the interim analysis (IA) and the DMC safety reviews. The DMC will review unblinded data during safety reviews and the IA. A limited team at Boston Pharmaceuticals will review unblinded results from the Phase 1b MAD portion during the IA to determine the dose that will be used for the Phase 2 POC portion of the study. Details regarding maintenance of the blinding and content of data reviews will be described in the DMC charter or related study documentation.

### 3.3. Sample Size Considerations

Sample size in the Phase 1b MAD part of the study is based on operational consideration.

The sample size in the Phase 2 POC study is based on the primary endpoint, SRI-4 Response at Day 210. Approximately 156 additional patients will be randomized in a 2:1 ratio to BOS161721 versus placebo to achieve 132 evaluable patients in the FAS. This assumes 24 patients will drop prior to having received treatment and an evaluable post-baseline efficacy measure. Enrollment and randomization will be monitored in a blinded fashion and increased if needed to ensure at least 132 patients are randomized into the FAS.

A total of 132 patients randomized provides more than 80% power to detect a treatment difference of 25% in SRI-4 response rates at Day 210, based on a targeted 2-sided significance level of 10% and using a 2-sided Pearson's chi-squared test. This assumes a response rate of 65% for BOS161721 and 40% for placebo, where missing data at Day 210 is carried forward

Sponsor: Boston Pharmaceuticals, Inc.  
Protocol Number: BOS161721-02  
SAP Version and Date: Version 2.0, 29Nov2018

from most recent non-missing result and patients are treated as a non-responder if a prohibited medication defined as a medication failure occurs.

### 3.4. Data Monitoring Committee (DMC)

This study will use an external DMC. The DMC is an independent committee established to provide oversight of safety considerations in the study and to provide advice to the sponsor regarding actions the committee deems necessary for the continuing protection of enrolled patients and those yet to be recruited to the trial as well as for the continuing validity and scientific merit of the study results. The DMC is charged with assessing such actions in light of an acceptable benefit/risk profile for BOS161721. The recommendations made by the DMC (i.e., dose escalation, etc.) will be forwarded to the sponsor for final decision. The sponsor will forward such decisions, which may include summaries of safety data which are not endpoints, to regulatory authorities, as appropriate.

The sponsor will appoint a DMC for the periodic review of available study data. The DMC is an independent group of experts that advises the sponsor and the study investigators. The members of the DMC serve in an individual capacity and provide their expertise and recommendations. The primary responsibilities of the DMC are to (1) periodically review and evaluate the accumulated study data for participant safety, study conduct, and progress, (2) make recommendations to the sponsor concerning the continuation, modification, or termination of the study and (3) suggest dose for POC portion of the study as described in the study protocol.

The DMC considers study-specific data as well as relevant background knowledge about the disease, test agent, or patient population under study. The DMC is responsible for defining its deliberative processes, including event triggers that would call for an unscheduled review, stopping guidelines, unmasking (unblinding), and voting procedures prior to initiating any data review. The DMC is also responsible for maintaining the confidentiality of its internal discussions and activities as well as the contents of reports provided to it.

The DMC will have access to unblinded treatment information during the clinical trial. Details regarding management and process of this committee are found in the DMC Charter.

The DMC may recommend termination of BOS161721 treatment arm or the entire BOS161721 MAD/POC trial for any safety concern that is felt to outweigh potential benefits. The recommendation must be supported by the sponsor as indicated in the DMC Charter.

### 3.5. Interim Analysis (IA)

One interim analysis is planned for this study and will be conducted at the time of the POC decision for dose selection. The POC dose will be selected based on the MAD data. Since there is no IA during the POC part of the study, there is no impact on the type 1 error.

Interim analysis outputs will be a subset of those to be performed for the final analysis.

### 3.6. Timing of Analyses

The following analyses are planned:

- An IA will be performed during the last cohort of the MAD portion to determine dose selection for the POC portion.
- The final analysis will be performed when all patients have either completed the POC safety follow up or withdrawn from the study.
- Safety analyses will be performed for DMC reviews throughout the study to evaluate dose escalation decisions and accumulating safety data. The frequency and details of the content and format of the safety review meetings are described in the DMC charter and SAP/mock shells.

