### 10.1. Adverse Events

AEs will be collected and recorded for each patient from the date of the first dose of study drug until the end of their participation in the study, including the safety follow up period. Severity of adverse events will be graded by the investigator according to National Cancer Institute Common Terminology Criteria for Adverse Events (NCI CTCAE) version 4.03. AEs will also be assessed for relationship to study drug, and seriousness. Adverse events will be marked as AESIs, dose-limiting toxicities (DLTs), or injection site reactions (ISRs), where applicable. AEs will be considered treatment-emergent adverse events (TEAEs) if they started any time after first dose or if the year, month and day of start date were missing. Any missing severity assessments will be assumed to be Grade 3, missing relationship assessments will be assumed to be related, and missing seriousness assessments will be assumed as serious.

Sponsor: Boston Pharmaceuticals, Inc.

Protocol Number: BOS161721-02

SAP Version and Date: Version 3.0, 13Nov2020

An overview of TEAEs will be produced, including counts and percentages of patients with any incidences of TEAE, TEAEs related to study treatment, SAEs, SAEs related to study treatment, any CTCAE grade 2 or higher TEAEs, any CTCAE grade 2 or higher TEAEs related to study treatment, any CTCAE grade 3 TEAEs, any CTCAE grade 3 or higher TEAEs related to study treatment, any CTCAE grade 4 TEAEs, any CTCAE grade 4 or higher TEAEs related to study treatment, TEAEs leading to study treatment discontinuation, treatment related TEAEs leading to study treatment discontinuation, TEAEs of special interest, related TEAEs of special interest, DLTs, related DLTs, TEAEs resulting in death, related TEAEs resulting in death, and injection site reactions. The maximum CTCAE grade (Grades 1-5) will also be included on the summary table.

Adverse events will be coded based on the MedDRA. Patients will be counted once per SOC (and likewise for PT within SOC). TEAEs will be summarized by SOC and PT in descending order of overall incidence of SOC (and PT within SOC). The MedDRA version used is defined in the study data management plan.

Summaries of adverse events by SOC and PT will include the following types:

- TEAEs;
- TEAEs related to study treatment;
- SAEs;
- Related Serious TEAEs;
- CTCAE Grade 3 or higher TEAEs;
- CTCAE Grade 3 or higher TEAEs related to study treatment;
- TEAEs leading to treatment discontinuation; and

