### **5.8. Treatment Group Display**

Treatment groups will be displayed with the following columns. See the mock shells for additional details and a visual representation of the treatment group display.

- Phase 1b MAD: Cohort 1 BOS 20mg
- Phase 1b MAD: Cohort 2 BOS 60mg
- Phase 1b MAD: Cohort 3 BOS 120mg
- Phase 1b MAD: Placebo

- Phase 1b MAD: Total BOS (All patients treated with BOS161721, excludes placebo)
- Phase 2 POC: BOS <dose> where <dose> is the value determined during the IA
- Phase 2 POC. Placebo
- Overall: Total BOS <dose>mg where <dose> is the common dose between the Phase 1b MAD and Phase 2 POC portions of the study (to be determined during the IA). If a common dose is not determined, this column will be omitted.
- Overall: Total BOS (Patients treated with BOS161721 in MAD and POC, excludes placebo)
- Overall: Total Placebo (Placebo patients in MAD and POC, excludes patients treated with BOS161721)

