### 10.1. Adverse Events

Adverse events (AEs) will be collected and recorded for each patient from the date of the first dose of study drug until the end of their participation in the study, including the safety follow up period. Severity of adverse events will be graded according to National Cancer Institute

Sponsor: Boston Pharmaceuticals, Inc.  
Protocol Number: BOS161721-02  
SAP Version and Date: Version 2.0, 29Nov2018

Common Terminology Criteria for Adverse Events (NCI CTCAE) version 4.03. AEs will also be assessed for relationship to study drug, and seriousness. Adverse events will be marked as adverse events of special interest (AESIs), dose-limiting toxicities (DLTs), or injection site reactions (ISRs), where applicable. AEs will be considered treatment-emergent adverse events (TEAEs) if they started any time after first dose or if the start date was missing. Any missing severity assessments will be assumed to be Grade 3, missing relationship assessments will be assumed to be related, and missing seriousness assessments will be assumed as serious.

An overview of TEAEs will be produced, including counts and percentages of patients with any incidences of TEAE, TEAEs related to study treatment, Serious adverse events (SAEs), SAEs related to study treatment, CTCAE grade 2 or higher TEAEs, CTCAE grade 2 or higher TEAEs related to study treatment, CTCAE grade 3 TEAEs, CTCAE grade 3 or higher TEAEs related to study treatment, CTCAE grade 4 TEAEs, CTCAE grade 4 or higher TEAEs related to study treatment, TEAEs leading to study treatment discontinuation, Related TEAEs leading to study treatment discontinuation, TEAEs of special interest, Dose-limiting toxicities, TEAEs resulting in death, and injection site reactions.

Adverse events will be coded based on the Medical Dictionary for Regulatory Affairs (MedDRA) for reporting by system organ class (SOC) and preferred term (PT) in descending order of overall incidence. The MedDRA version used is defined in the study data management plan.

Summaries of adverse events by SOC and PT will include the following types:

- TEAEs;
- TEAEs related to study treatment;
- SAEs;
- CTCAE Grade 3 or higher TEAEs related to study treatment;
- TEAEs leading to treatment discontinuation; and
- Dose-Limiting Toxicities
- TEAEs of Special Interest

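### Crude AE percentages at the dose-selection interim analysis would cover unequal follow-up across MAD cohorts and tend to favour 120 mg

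*SAP*

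**What the plan says.** The following is from SAP v2.0 unless stated; v1.0 has the same text on timing.

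- **Timing (Section 3.6):** "An IA will be performed during the last cohort of the MAD portion to determine dose selection for the POC portion". No data cut and no minimum follow-up for the last cohort are given.
- **Content (Section 3.5):** "Interim analysis outputs will be a subset of those to be performed for the final analysis". The AE tables in the subset are not named.
- **Stagger (Section 3.1.1):** Cohort 2 (60 mg) opens once all 6 Cohort 1 (20 mg) patients have had two doses plus two weeks. Cohort 3 (120 mg) opens "after 8 of the 12 patients in Cohort 2 have received 2 doses and have completed 2 weeks of follow up". A DMC review precedes each step.
- **AE summaries (Section 10.1):** "An overview of TEAEs will be produced, including counts and percentages of patients with any incidences of TEAE". An event counts if it starts at any time after first dose. Section 10.1 of v3.0 keeps the same measure. Section 4 includes all data up to completion or withdrawal, whatever the length of treatment.
- **Columns (Section 5.8):** one column per dose and a single pooled column, "Phase 1b MAD: Placebo".
- **Use (Section 3.1.2):** "Dose selection will be based on the DMC and sponsor's assessment of safety, tolerability, immunogenicity, and PK and PD data". Section 2.1 makes AE incidence and severity a primary endpoint of the MAD part.

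The text at hand plans no exposure-adjusted AE rate, no time-to-first-AE analysis and no common follow-up window.

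**The concern.** At the final analysis crude percentages are a reasonable summary, because every cohort has been scheduled through Day 270. At an analysis run while Cohort 3 is ongoing, the 20 mg column has had the longest time to accumulate events and the 120 mg column the shortest. A percentage of patients with any event grows with follow-up, so the column with least follow-up tends to show the lowest figure even when dose has no effect.

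The pooled placebo column mixes patients from all three cohorts and matches the follow-up of no dose column. Summaries of C-SSRS or ECG findings at any post-baseline time would share the problem if they enter the interim subset.

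Safety is a named input to the choice of the Phase 2 dose. A dose-related excess of AEs at 120 mg could be hidden or appear reversed in the table that the unblinded reviewers read first.

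**Working it through.** **Reproducing the plan's own figure.** The plan bases dose selection on 30 MAD patients: 6 + 12 + 12 = 30, of whom 5 + 9 + 9 = 23 are active and 1 + 3 + 3 = 7 placebo. This agrees. The plan gives no figure for follow-up per cohort at the interim analysis.

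**Inputs from SAP v2.0.** Doses fall on Days 0, 30, 60, 90, 120, 150 and 180, with follow-up to Day 270 (Section 3.1). Each step of the stagger needs two doses plus two weeks (Section 3.1.1).

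**Lag.** On nominal days each step takes 30 + 14 = 44 days. The last Cohort 1 patient therefore leads the first Cohort 3 patient by at least 44 + 44 = 88 days. Eight of the 12 Cohort 2 patients lead by at least 44 days; the other four may lead by less. DMC review time adds to both lags.

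**Follow-up.** Let t be the days since Cohort 3 started. Taking the minimum lags, follow-up is t at 120 mg, min(270, t + 44) at 60 mg and min(270, t + 88) at 20 mg.

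**Assumptions, not in the documents.** The AE hazard is constant and equal in all cohorts, and 50% of patients have an event by Day 270 (range 30% to 70%). Each cohort is treated as having one follow-up time.

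**Formulas.** Hazard h = -ln(1 - 0.5)/270. Expected crude percentage = 1 - exp(-h × follow-up). The true rate ratio at 120 mg that would appear as no difference is (follow-up of the comparator)/t, which does not depend on h.

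| Cohort 3 at day t | Follow-up 20/60/120 mg (days) | Expected crude % with no dose effect, 20/60/120 mg | Ratio hidden vs 20 mg | Ratio hidden vs 60 mg |
|---|---|---|---|---|
| 44 | 132/88/44 | 28.7/20.2/10.7 | 3.00 | 2.00 |
| 90 | 178/134/90 | 36.7/29.1/20.6 | 1.98 | 1.49 |
| 120 | 208/164/120 | 41.4/34.4/26.5 | 1.73 | 1.37 |
| 180 | 268/224/180 | 49.7/43.7/37.0 | 1.49 | 1.24 |
| 210 | 270/254/210 | 50.0/47.9/41.7 | 1.29 | 1.21 |
| 270 | 270/270/270 | 50.0/50.0/50.0 | 1.00 | 1.00 |

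At t = 90 the expected percentages are 21.0/16.2/11.2 with 30% incidence and 54.8/45.0/33.1 with 70%.

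**Pooled placebo.** At t = 90, mean follow-up is (178 + 3 × 134 + 3 × 90)/7 = 121 days against 90 at 120 mg, a ratio of 1.35. At t = 210 it is (270 + 3 × 254 + 3 × 210)/7 = 237 days against 210, a ratio of 1.13.

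**Chance.** With 9 against 9 active patients, equal hazards, 50% incidence and t = 90, the 120 mg percentage is below the 60 mg percentage with probability 0.56, equal with 0.20 and above with 0.24. With equal 44-day windows, below and above are equally likely (0.34 each).

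**Dependence on AE timing.** If every AE started within 30 days of first dose, the bias would vanish once all patients had 30 days of follow-up.

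**The case against.** **Version.** The timing text is from v2.0, and Section 3.6 of v3.0 is not in the text at hand, so a data-cut rule may have been added. This limits the point to v1.0 and v2.0 on timing. Section 10.1 of v3.0 still uses crude percentages, and Sections 10.2, 10.3.3 and 10.3.4 still refer to interim outputs, though only to listings.

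**Content.** The interim AE tables are inferred. Section 3.2 leaves the content of data reviews to the DMC charter or related documents. That stands as a caveat. However, Section 3.5 ties the interim outputs to the final set, and that set contains no follow-up-adjusted AE summary.

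**Other displays.** By-patient listings, by-visit laboratory and ECG tables, and exposure summaries can alert reviewers to unequal follow-up. None corrects the AE percentages. Exposure in Section 6.7 is last dose date minus first dose date plus 1. With Cohort 1 at Day 270 and Cohort 3 at Day 182, both show 180 - 0 + 1 = 181 days despite an 88-day gap in follow-up.

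**Decision process.** No test or formal rule hangs on these percentages, and immunogenicity, PK and PD also count. That is right, and it lowers the stakes. The numbers are also small: at t = 90, 36.7% of 5 is 1.8 patients and 20.6% of 9 is 1.9.

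**A stronger reading.** A reader might infer that 120 mg will look safer whatever the date of the analysis. The documents do not support that. The interim date is not fixed, the gap closes as Cohort 3 approaches Day 270, AE timing is unknown, and chance is large with 5 to 9 patients per dose.

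**Conclusion.** The point holds for v2.0 and v1.0 as a correctable weakness in the interim safety summaries. Any crude AE percentages shown at the dose-selection analysis would compare columns with unequal follow-up, and the expected tilt is towards 120 mg.

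Its size depends on an interim date that the plan does not give. Under an equal constant hazard and the minimum lags, the concealed rate ratio is about 2.0 against 20 mg and 1.5 against 60 mg at Day 90 of Cohort 3. It falls to about 1.3 and 1.2 at Day 210 and to none at Day 270. With AEs concentrated soon after first dose there is little bias at any of these dates. The conclusion concerns how safety is summarised and takes no position on which dose to choose.

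**What to change.** For the interim analysis:

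1. State the data cut.
2. For each dose column and for placebo, add first-event rates per patient-time at risk, or Kaplan-Meier cumulative incidence, and print median follow-up in the column header.
3. Add an AE table over a common window ending at a pre-stated study day, showing how many patients in each column reached it. The day should not be set by the newest Cohort 3 patient, because the window could then shrink to a few days.
4. Keep the all-data percentages as a secondary display, so that later events in Cohorts 1 and 2 remain visible.

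The cost is SAP and mock-shell wording and some programming, with no new data or patients. If the analysis has already been run, the same summaries can be produced from existing data. The limits should be stated beside the tables: rates from 5 to 9 patients are imprecise, patient-time rates are fully comparable only under a roughly constant hazard, and the common window omits later events.
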